### Transcranial magnetic stimulation (TMS) measures of Cortical Excitability

TMS is a widely employed non-invasive brain stimulation (NIBS) technique to characterize neurophysiological function underlying neuropsychiatric illnesses [39], including markers of cortical excitability and plasticity that can elucidate the neurobiology of drug action [40]. TMS paradigms include measurements of motor evoked potentials (MEP) with surface electromyography (EMG) applied to hand muscles such as the abductor pollicis brevis (APB) after applying single or paired TMS pulses on the motor cortex [41, 42]. The motor cortex is an extensively studied target area for neurophysiological studies because changes in motor activation and excitability can be readily and reliably assessed by MEP [42]. **MEP amplitude, cortico-motor threshold (MT) and intra-cortical facilitation (ICF)** are commonly reported measures of cortical excitability function [42]. The MEP amplitude is measured as the average response to a series of TMS pulses applied at a consistent TMS intensity [43]. MEP amplitude is thought to be dependent on NMDA and voltage gated channels and thus modulated by NMDA and GABAergic drugs and a reliable measure of the excitatory/inhibitory balance of cortical pyramidal cells [39]. MT is a measure of corticospinal excitability and depends on the excitability of axons and that of synaptic connections at corticospinal level [40, 42]. Voltage-gated sodium (Na) channels regulate axon excitability and NMDA regulates fast excitatory synaptic neurotransmission in the neocortex [39]. Anticonvulsants with Na channel blocking properties increase MT. Ketamine, a NMDA antagonist, paradoxically decreases MT [44]. ICF assessments by TMS involve pairing a subthreshold (80% of RMT) conditioning stimulus followed by a suprathreshold test stimulus, with an interstimulus interval of 10–20 ms [39, 45]; such pre-conditioning facilitates (i.e. increases amplitude) the MEP. ICF is thought to index NMDAR-mediated excitatory neurotransmission in the cortex [39, 46] though GABA and other neuromodulators may also contribute to ICF. A **review of TMS studies of cortical excitability** in patients with MDD indicated no significant differences in cortical excitability measures [47]. However, there were cortical inhibitory deficits as measured by intra-cortical inhibition and silent cortical period, both thought to be linked GABA function. Interestingly, Levinson et al. found increased resting motor threshold (RMT) in TRD compared with unmedicated MDD patients, medicated/ euthymic MDD patients, and healthy subjects [48]. While chronic (30 days) administration of paroxetine in healthy subjects induced a significant increase in ICF, single intravenous administration of serotonergic antidepressants, citalopram and clomipramine reduced motor cortical excitability in TRD patients [49]. These findings raise the intriguing question whether any reductions in cortical excitability in TRD patients could be ameliorated by Ketamine's ability to increase cortical excitability.

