Exploratory Aim: To investigate Ketamine's acute excitatory glutamatergic effect on cortex as indexed by the ASSR. The first goal of the study is to deploy auditory steady state response (ASSR) and gamma band oscillations as a marker of Ketamine's early excitatory effect on cortex. We previously studied the feasibility of quantifying the effect of pharmacological manipulations on cortical ASSR power. We studied the effect of amphetamine, which increases synaptic dopamine neurotransmission. Twelve healthy subjects (mean age  $30.3 \pm 10$ , M:F 7:5) took part in a double-blind, cross-over, placebo-controlled study of single-dose amphetamine (0.5 mg/kg) administration. Subjects performed the ASSR task, involving auditory click trains consisting of binaural presentations of 1 ms duration tones repetition frequencies of 40 Hz, 30 Hz, or 20 Hz. To ensure attention to stimuli, click trains were presented as an oddball paradigm. Electroencephalographic (EEG) data during task performance were collected on a 128 channel Geodesic Sensor Net. Off-line de-noising and averaging will be performed with EEGLAB (62), and wavelet analyses with Brain Vision Analyzer. The average evoked gamma power was derived for the 40 Hz stimuli over the interval 225–525 ms after stimulus onset. Amphetamine showed decreases in gamma power specifically to the 40 Hz stimuli ( $t=2.3$ ,  $p<.05$ ,  $d_z=0.66$ ). Time frequency plots of gamma power after amphetamine for 40 Hz stimuli demonstrated amphetamine induced decreased gamma power. ASSR-EEG paradigm may be well-suited to tracking Ketamine induced modulations in gamma oscillations as implemented in this project

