**Cortical Excitability-TMS procedure:** TMS-EEG will be performed at 4 hours, 24 hours and 7 days after the infusion. Patients will be seated in an armchair with elbow semi-flexed; the forearm pronated and fully relaxed. Participants will be given ear plugs for comfort and noise safety. A MagVenture MagPro X100 transcranial magnetic stimulator system with a figure-of-eight coil (diameter=70 mm for each loop) will be placed tangentially over the scalp overlying the primary motor cortex and DLPFC. The stimulator is paired with Localite neuronavigation system which allows precisely localized stimulus application and its integration also allows

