external control of the MagPro system. EMG readings may be obtained from the APB muscle. TMS stimulation will be applied to the corresponding region of the contralateral primary motor cortex. The optimal coil position will be determined by moving the coil in 1-cm increments over the motor cortical area while delivering magnetic pulses and by observing maximal contraction of the contralateral APB. The procedure may be repeated for the opposite hemisphere. The main purpose of this study is to examine the cortical excitability measures after Ketamine. Resting motor threshold (RMT) is defined as the stimulation intensity eliciting an MEP greater than 0.5 mV in 5 of 10 trials with a relaxed APB. Intra-cortical facilitation (ICF) is defined as subthreshold conditioning stimulus set at 80% of resting MT calibrated to produce an average MEP of 0.5- to 1.5-mV peak-to-peak amplitude in the contralateral APB. A suprathreshold test stimulus follows conditioning stimulus between 10-20 milliseconds (ms) (55). Conditioning stimuli may be delivered to left Dorsolateral Prefrontal Cortex (DLPFC) or Brodmann Area 6 or Motor cortex prior to the test stimulus in 1 of 3 random inter-stimulus intervals 10 ms (ICF-10), 15 ms (ICF-15), and 20 ms (ICF-20) for ICF measures. The sequence of administration will be counterbalanced to reduce order effects. For ICF, the change in test stimulus MEP amplitude of each inter-stimulus interval was expressed as a percentage of the mean unconditioned MEP amplitude (55). TMS will be applied concurrently with EEG recordings. **EEG/EMG Acquisition and Analysis** - EEG sessions will be conducted in a sound-attenuated room lit with a low-level ambient light. EEG Brain Products Brain Amp MRPlus 64 channel system is used to acquire EEG data. EEG signals are recorded with a 64 channel cap at a high sampling rate (500 Hz) from the entire scalp, with signals amplified by a shielded, MR-compatible amplifier. The software, Brain Vision Recorder, will be used to coordinate EEG recordings with EPrime. Continuous data will be filtered off-line with a .2- to 100-Hz bandpass filter with a 60-Hz ideal notch filter. ASSR Epochs are defined as -500 to 1000 ms relative to stimulus onset adjusted to a -350 to -150-ms prestimulus baseline. Ocular and ECG artifacts will be removed with ICA-based detection and correction methods (EEGLab); [59]. Data will be re-referenced to average reference. EMG data will be obtained using the Brain Amp ExG amplifier which allows for up to 8 simultaneous bipolar recordings at a 5-kHz sampling rate via the same software as EEG data. MEP epochs will be defined as -200 to 300 relative to stimulation. ICF trials will be time adjusted to align the second pulse with single pulse trials, and MEP amplitudes will be determined as the peak to be difference identified between 10 and 50 ms post-TMS pulse. Software and hardware for the analysis of EEG/EMG data, include state-of-the-art analytic and statistical packages (e.g. EEGLab, Brainstorm, Matlab, and SPSS).

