### **Power Analysis**

Sample size justification: For the current proposal, our power calculation is based on our prior data on ASSR (Komek K et. al 2012) after pharmacological manipulation with effect size estimate of 0.9 and is guided by a previous study which used intravenous antidepressant clomipramine in TRD patients and found decreased motor excitability (increased RMT)(Minelli A et.al 2010) with large effect size estimate of Cohen's  $d = 1.2$ . For this project proposal, even if we assume a lower effect size of  $d=0.9$ , assuming a two-sided  $\alpha < 0.05$ , a sample of  $N=15$ , randomized in a cross-over design, participants provides 95% power to detect a difference between the two groups. Our sample size of 20 subjects would be sufficient event at attrition of 20%.

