### **Statistics**

Normality assumptions for continuous variables will be examined. Where appropriate, outliers will be winsorised and log, square root or reciprocal transformations applied to achieve normality if appropriate. If normality cannot not been achieved, either untransformed or dichotomized scores were used. Baseline characteristics will be compared between responders and non-responders with the Mann-Whitney U test for continuous variables and the chi-square test for categorical variables. Changes between two time-points for continuous variables were tested with paired t tests, and associations between continuous variables will be quantified with the Spearman correlation coefficient. Random effects models will be performed to quantify changes in clinical score and its component items over time and to compare temporal differences between eventual responders and non-responders. Splines will be used to determine differences in the pattern of response over time among all patients and to identify the time at which there was no additional improvement in depressive symptoms. Additionally, the relationship between response status between baseline and end of study calculating sensitivity, specificity, and positive and negative predictive values will be reported. Time to relapse for patients who met response criteria at end point will be estimated with the Kaplan-Meier method. Analyses will be performed with IBM SPSS Statistics (version 19; SPSS, Chicago, Illinois) and SAS (version 9.2; SAS, Cary, North Carolina).

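### No primary TMS contrast is named, so cortical excitability may be tested up to 15 times at an uncorrected 5%; the chance of a false finding is then about 37% at an assumed correlation of 0.5 (about 22 to 47% over correlations of 0.8 to 0.3)

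*Combined protocol and SAP*

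**What the plan says.** **Purpose.** The Cortical Excitability-TMS procedure (Study Design and Procedure) gives the examination of excitability measures after ketamine as the study's main purpose. The Objectives section puts the interest in the DLPFC, using TMS-EEG.

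**Measures.** The background section on TMS says of MEP amplitude, motor threshold and ICF that they "are commonly reported measures of cortical excitability function". The TMS procedure defines RMT and ICF. It uses "1 of 3 random inter-stimulus intervals 10 ms (ICF-10), 15 ms (ICF-15), and 20 ms (ICF-20) for ICF measures" and expresses the conditioned response separately for each interval, as a percentage of the unconditioned MEP. The conditioning site may be left DLPFC, Brodmann Area 6 or motor cortex, and the opposite hemisphere may be repeated.

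**Times.** "TMS-EEG will be performed at 4 hours, 24 hours and 7 days after the infusion". The Summary adds a baseline TMS-EEG session on Day 2.

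**Analysis.** For change in continuous variables, the Statistics section says: "Changes between two time-points for continuous variables were tested with paired t tests". Its random effects models are named for the clinical score and its items only. The Data monitoring plan refers to primary outcomes in the Statistical Plan, but the Statistics section names none.

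**Level and size.** The level appears only in the Power Analysis, in a clause beginning "assuming a two-sided", with alpha 0.05. The 95% power is for one comparison at N=15. On dropout it says: "Our sample size of 20 subjects would be sufficient event at attrition of 20" per cent.

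**The concern.** The plan has one 5% level, a power figure for one comparison, and several measures, intervals and times that could each supply that comparison. Nothing says which one answers the question. An isolated p<0.05, for example ICF-15 at 24 hours, could be reported as evidence that ketamine changes cortical excitability. The 5% error rate would not apply to that conclusion, because the result would have been picked from a family of tests. The study is open-label with a single arm and 16 to 20 evaluable patients, so little else in the design would expose a chance finding.

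**Working it through.** **1. The plan's own figure.** The Power Analysis states 95% power at d=0.9, N=15, two-sided 0.05. Reading d as the paired (within-patient) effect size:
- normal approximation, two-sided: Φ(0.9·√15 − 1.96) = Φ(1.526) = 93.7%;
- exact noncentral t, one-sided: 95.2%;
- exact noncentral t, two-sided: 89.9%.

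So 95% is reproduced approximately by the normal formula or by a one-sided t test. Either way it is the power of one test. The plan gives no family-wise error rate to reproduce.

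**2. Number of tests (a reading, not a stated figure).**
- RMT, MEP amplitude, ICF-10, ICF-15 and ICF-20 are 5 variables; 5 × 3 post-infusion times = 15 contrasts with baseline.
- With one ICF value instead of three: 3 × 3 = 9.
- One measure only: 1 × 3 = 3.

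**3. Independent tests.** The chance of at least one p<0.05 under no effect is 1 − 0.95^k:
- k=3: 14.3%
- k=9: 37.0%
- k=15: 53.7%

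**4. Correlated tests.** The contrasts are not independent. Three changes share one baseline. With equal variance σ² and equal correlation ρ between visits, Var(Yj − Y0) = 2σ²(1 − ρ) and Cov(Yj − Y0, Yk − Y0) = σ²(1 − ρ), so two changes in the same measure correlate 0.5 whatever ρ is. The three ICF values also share one denominator. The documents give no correlation between measures, so a range is needed.

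Null trials were simulated with n=16 (20 enrolled × 0.8), multivariate normal change scores with a common correlation r, two-sided paired t tests at 5%, and 40,000 replicates. Chance of at least one p<0.05:

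| Contrasts | r=0 | r=0.3 | r=0.5 | r=0.8 | r=0.9 |
|---|---|---|---|---|---|
| 3 | 14% | 14% | 13% | 10% | 9% |
| 9 | 37% | 33% | 28% | 17% | 13% |
| 15 | 54% | 46–47% | 37% | 21–22% | 15% |

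Results at n=20 are nearly the same (15 contrasts: 37% at r=0.5, 22% at r=0.8). A measure-by-time structure for the 15 contrasts gives 42% with 0.5 between measures and 0.5 between times, and 25% with 0.8 for both.

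**5. Power if the error is controlled.** Exact two-sided paired t test, n=16. The effect sizes are 0.9 (Power Analysis) and 0.66 (the amphetamine ASSR result in Objectives).

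| Level | d=0.9 | d=0.66 |
|---|---|---|
| 0.05 (one primary test) | 92% | 69% |
| 0.05/9 = 0.0056 | 64% | 32% |
| 0.05/15 = 0.0033 | 56% | 25% |

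**The case against.** The strongest reply is that this is a small first study. The Data monitoring plan calls the trial small and initial, another section speaks of piloting new approaches, and the neurophysiological assessment is headed optional. Formal family-wise control is not obligatory in such a study, and labelling the tests exploratory would meet the concern. That much stands, and the fix allows for it. But the plan does not apply that label to TMS: only the ASSR aim, on ketamine's "acute excitatory glutamatergic effect on cortex as indexed by the ASSR", carries it. The Power Analysis also argues from a 5% level and 95% power.

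Four stronger readings are tempting, and the documents do not support them.
- **That 37% is the trial's error rate.** It needs 15 tests and r=0.5, and the plan gives neither. The Statistics section does not list the variables to be tested, so one t test per measure and time is the natural reading, not an explicit statement.
- **That the family is larger still, at 33 tests over three conditioning sites, with an error near 55%.** The sites are worded as alternatives that may be used; nothing says every patient receives all three.
- **That the TMS tests are declared confirmatory.** No passage says so. The aim labels are weak evidence, since the exploratory ASSR aim is also called the first goal.
- **That RMT must be the primary measure because the Power Analysis cites an effect size for it.** RMT is a motor-cortex measure and does not address the stated DLPFC objective.

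**Conclusion.** The point holds in this form: the plan names no primary TMS contrast and no rule for multiple tests, although excitability is its main purpose and it defers to primary outcomes that the Statistics section never lists. Every family examined, down to one measure at three times, exceeds the 5% level. The size rests on the assumed number of tests and correlation. This is more than missing detail, because following the plan as written allows any of these contrasts to be claimed at 5%. It should be corrected, and doing so is cheap.

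**What to change.** In the Statistics section:

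1. Name one primary TMS contrast: one measure, one site, and one post-infusion time against baseline, tested at two-sided 5%. The sponsor chooses it to match its stated objective. If RMT is chosen, its MEP criterion must first be reconciled (50 µV in Objectives, 0.5 mV in the TMS procedure).
2. Fix that choice before any post-infusion TMS data are examined. Data lock is too late in an open-label, single-arm study, because results can be seen throughout.
3. Declare all other TMS measures, ICF intervals, times, sites and the second hemisphere exploratory, reported with estimates and confidence intervals and without significance claims.
4. If they are to be tested formally instead, test them only after the primary contrast is significant, with Holm or a permutation max-t procedure, so that the total error stays at 5%. The gate matters: a full 5% on the primary contrast plus ungated Holm on the other 8 of 9 gives a total error of about 8 to 9% under no effect, at correlations of 0.5 to 0.3.

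Averaging the three ICF intervals would shorten the list, but nothing in the documents supports it; the pilot data used 10 ms only.

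**Cost.** A few sentences, with no new data or patients. The primary test keeps the unadjusted power shown above (92% at d=0.9, 69% at d=0.66, n=16). The loss falls on the non-primary contrasts. If tested formally, they have in the Bonferroni worst case over 9 to 15 contrasts about 64 to 56% power at d=0.9 and 32 to 25% at d=0.66, before allowing for the gate. Holm and max-t are usually somewhat better than Bonferroni. If the primary contrast is not significant, no other TMS contrast can be claimed.

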7. **Young Mania Rating Scale (YMRS):** This is a well-established clinical severity rating scale for manic symptoms that has adequate inter-rater reliability and internal consistency (Young et al., 1978). Frequency: Before the start of the study and at 4 hours, 24 hours and 7 days after infusion. (Changed based on the PI).
8. **Positive and Negative Affect Schedule (PANAS):** the PANAS comprises two mood scales, one that measures positive affect (PA) and the other which measures negative affect (NA). Used as a psychometric scale, the PANAS can show relations between positive and negative affect with personality stats and traits. Ten descriptors are used for each PA scale and NA to define their meanings. Participants in the PANAS are required to respond to a 20-item test using 5-point scale that ranges from very slightly or not at all (1) to extremely (5). This scale may be administered prior to and following each infusion to assess acute changes in mood. Frequency: Before the start of the study and at 4 hours, 24 hours and 7 days after infusion. (Changed based on the PI).
9. **The World Health Organization Quality of Life (WHOQOL)-Brief :** this scale is patient-reported and measures the degree of enjoyment and satisfaction experienced by subjects in various areas of daily functioning (*Endicott*

*et al.*, 1993). Frequency: Before the start of the study and at 4 hours and 24 hours after infusion. (Changed based on the PI).

**10. Hamilton Depression Rating Scale (HDRS):** a multiple item questionnaire used to provide an indication of depression, and as a guide to evaluate recovery. Frequency: Before the start of the study and at 4 hours, 24 hours and 7 days after infusion. (Changed based on the PI).

**11. Hollingshead Socioeconomic Status:** This scale is patient-reported and indication of socioeconomic status. Frequency: At the discretion of the PI.

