### Summary

We will pre-screen potential participants over the phone to minimize the invitation to non-eligible participants. During the screening visit, we will screen patients for eligibility. Patients will then arrive for their study Day # 2(Baseline), when they will get blood draws (optional), complete questionnaires and undergo TMS-EEG. Patients will come to our inpatient psychiatric hospital facility on the another day (Day # 3) , where they will be given ketamine by the study nurse. During the infusion, patients will be asked constantly about "how they feel" and will be monitored continuously from psychiatric nurse and the attending Anesthesiologist. EKG and pulse-oximetry will be monitored throughout the procedure to check for hemodynamic changes. After the completion of 40 min infusion, patients will rest for two – four hours under the observation of clinical nurse and, reassessed again by psychiatrists at 2 hours after infusion. Patients may be undergoing EEG/ASSR at 10minutes, 40 minutes and at 4 hours after infusion and blood tests after infusion(40 minutes) and 2-4 hours after infusion. Patient will then

have undergo TMS-EEG & EMG at 4 hours. Patient will be discharged to a responsible adult who will accompany the patient home. Patients will be invited again for day #4 (24 hours after infusion), where they will have to complete TMS-EEG & EMG, EEG/ASSR(optional) and blood tests(optional). They will be invited again for just TMS 7 days after infusion. Patients may be contacted every day after the infusion by telephone to check on their physical and mood status and will be scheduled for a clinical visit with the psychiatrists on days 1, 4, and 7 for a follow up assessment of mental state.

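### With a day-7 end point, no scheduled depression rating remains from which to estimate time to relapse, and a responder comparison tested on the score that defines response would be circular

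*Combined protocol and SAP*

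**What the plan says.** The Statistics section plans four analyses that depend on response status or on the course of the depression score.

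- Relapse: "Time to relapse for patients who met response criteria at end point will be estimated with the Kaplan-Meier method".
- Trajectory: "Random effects models will be performed to quantify changes in clinical score and its component items over time", and also "to compare temporal differences between eventual responders and non-responders".
- Plateau: splines are to be used "to identify the time at which there was no additional improvement in depressive symptoms".
- Accuracy: "the relationship between response status between baseline and end of study calculating sensitivity, specificity, and positive and negative predictive values will be reported".

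Response, relapse and end point are not defined. The only place that ties clinical response to a scale is the gene-expression part of the optional blood tests, which uses the reduction in HDRS and gives no cut-off.

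Under Clinical assessment, HDRS and MADRS share one schedule: "Before the start of the study and at 4 hours, 24 hours and 7 days after infusion. (Changed based on the PI". The Summary describes the last visit differently: "They will be invited again for just TMS 7 days after infusion". It also mentions optional daily telephone checks and psychiatrist visits "on days 1, 4, and 7 for a follow up assessment of mental state", with no depression scale attached to either.

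**The concern.** Time to relapse needs repeated observation after the moment a patient is classed as a responder. If responders are identified at the last scheduled rating, that observation does not exist. A published relapse curve would then look like evidence on durability with no follow-up behind it.

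The trajectory comparison raises a different problem. If eventual responders are the patients whose score fell enough by day 7, the two groups must differ on that score at day 7. A test that includes the day-7 value can then report a distinct responder course even when all patients share one trajectory. The study looks for markers of response, so readers could take that result as a finding.

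**Working it through.** The documents give no figure for the relapse analysis or the responder comparison, so there is none to reproduce. The power calculation concerns ASSR and motor threshold and has no bearing here.

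**1. Ratings left after each possible end point.** Post-infusion ratings are at 4, 24 and 168 h (Clinical assessment, HDRS and MADRS).

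| End point | Later scheduled ratings | What can be estimated |
|---|---|---|
| Day 7 | 0 | Nothing: every responder is censored at time zero |
| 24 h | 1 (day 7) | One proportion; relapse known only to lie between 24 h and day 7 |
| 4 h | 2 (24 h, day 7) | A two-step, interval-censored curve |

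The accuracy sentence refers to the end of the study and the trajectory sentence to eventual responders. Both suggest day 7, but neither settles it.

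**2. Circularity.** Assumptions, none taken from the documents:
- baseline mean 24 (SD 4) and one mean trajectory shared by all patients;
- day-7 mean change -8, -9.5 or -11, with 4 h at 0.8 times and 24 h at 1.1 times that value;
- SD of change 3, 4, 6 or 8;
- response is a fall of at least 50% at day 7;
- trials with at least 3 patients in each group.

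The test is a random-intercept model with categorical time by responder (split-plot F) at alpha 0.05. N is 20, or 20 × 0.8 = 16 after the 20% attrition in the Power Analysis. With changes uncorrelated with each other and with baseline, the rejection rates are:

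| N | Day 7 included | Day 7 left out |
|---|---|---|
| 16 | 55% to 80% | 6% to 7% |
| 20 | 62% to 91% | 6% to 7% |

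Over all the correlations tried, shuffled responder labels give 4% to 7%. The excess in this table therefore comes from the defining score.

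With positive correlation between changes, the test rejects more often even when day 7 is left out: about 12% to 33% (N=16) and 12% to 42% (N=20) at correlation 0.5, and 33% to 70% and 41% to 82% at 0.7. Those rejections reflect real within-patient association between early and late change. They are not circularity.

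**3. Plateau.** The last two ratings are 168 - 24 = 144 h apart. A spline has no data inside that interval, so it cannot place a plateau there.

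**4. What the schedule can support.** Background Information cites 64% response and 21 of 47 patients still improved over 7 days. Assume that the 64% applies at 24 h and that nobody responds late.
- N=20: 0.64 × 20 = 12.8, about 13 responders at 24 h; 21/47 × 20 = 8.9, about 9 at day 7.
- Sustained response: 9/13 = 69%, exact (Clopper-Pearson) 95% CI 39% to 91%.
- A less favourable 7/13 = 54% has a CI of 25% to 81%.
- N=16: about 10 and 7, so 7/10 = 70% (35% to 93%).

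**The case against.** The strongest reply is that the end point is undefined and the PI may change the rating times, so a curve of some kind might be computed. That stands. A reader might infer that Kaplan-Meier is impossible on any reading, but this is strict only for a day-7 end point.

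A reader might also infer the absence of later follow-up from the five-visit count in the consent section or from the payment schedule. Neither shows it. The Summary's psychiatrist visit on day 4, if counted from the infusion, lies outside both. The stated subject duration of 2 to 3 weeks leaves calendar time after day 7 but puts no rating there. The argument rests on the rating schedule alone.

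On circularity, the Statistics section names neither the response scale nor the clinical score, and it specifies no test. If response were set on HDRS and the trajectory modelled on MADRS, the problem would shrink but not vanish, because both rate depression at the same visits. A purely descriptive comparison is legitimate, and so is a comparison limited to 4 h and 24 h.

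The accuracy sentence can be read literally to make baseline response the predictor. Nobody is a responder at baseline, so sensitivity would be 0 and the PPV undefined. That reading is uncharitable. The background stresses early response as a predictor, and 4 h and 24 h are the only ratings between baseline and day 7. This is a gap in wording and does not void the analysis. The spline point likewise concerns coarse resolution: a plateau before 24 h would not fall in the gap.

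**Conclusion.** The concern holds, with conditions. With a day-7 end point there is no scheduled follow-up for relapse. With 24 h there is one rating, and with 4 h there are two. Nothing in the documents commits to either earlier choice.

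The trajectory comparison is circular if response and trajectory use the same scale, the day-7 score is included and the difference is tested. The rates that isolate this are those at zero correlation, about 55% to 80% at N=16 and 62% to 91% at N=20. They depend on the assumed means, SDs and 50% cut-off. Higher rates at positive correlation should not be put down to circularity alone.

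These are secondary clinical analyses in a study whose stated goal is neurophysiological. The point should be fixed, but it does not undermine the main aim.

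**What to change.** 1. Name the response scale, the threshold and the end point, with response measured against the pre-infusion rating.
2. Replace the Kaplan-Meier sentence with the proportion of 24-h responders still in response at day 7, with an exact binomial CI. Keep every 24-h responder in the denominator. State in advance how patients removed for hospitalization (Protections against risk) are counted.
3. Do not test the responder-by-time difference with the defining score included. Show trajectories by responder status descriptively, or limit any comparison to 4 h and 24 h and call it early-late association. Keep the random-effects model of the score in all patients.
4. State that 4-h and 24-h response are the predictors of day-7 response in the accuracy analysis. The PPV of 24-h response is the same number as in item 2, so report it once.
5. Report the 24 h vs 4 h and day 7 vs 24 h contrasts in place of a time of no further improvement.
6. Reconcile the TMS-only description of the day-7 visit in the Summary with the day-7 ratings under Clinical assessment. If no day-7 rating is taken, the day-7 analyses drop out. Also reconcile the wording that implies several infusions (Study Design and Procedure, Blood Tests, Data Handling) with the single-dose description under Potential Risks.

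The cost is a rewording of the Statistics section and two reconciliations, with no new visits or data. The relapse-time claim is lost and the replacements are imprecise. In the N=20 example, specificity is 7/11 = 64% (31% to 89%), and each paired contrast has 80% power only for a standardized change of 0.66 (0.75 at N=16).
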